6.4 End of Treatment

Visit 6 (End of treatment visit 1)

At the end of the 12 week treatment period, subjects will be asked to return for testing. Subjects will be asked to return within 24 hours of taking their last study pill. The following tests and procedures will be performed:

- Ankle Brachial Index (ABI)
- GXT will be done to determine pain free and maximal walking distance
- A Walking Impairment Questionnaire (WIQ), a 36-item short-form health survey (SF-36), and Quality of Life Questionnaire (PAD-QOL) will be given
- Body height and weight will be measured using standard anthropometric procedures
- Total body lean and fat mass will be determined
- Blood pressure measurement and reading of recording on the blood pressure monitor.
- Review of daily diaries for any side effects.

- Collect and assess study medication.
- Women of child bearing potential will have a urine pregnancy test to verify they are not pregnant.

Visit 7 (End of treatment visit 2)

Visit 7 will occur within 48 hours of visit 6. At that visit the following tests and procedures will be done:

- 10 hour fasting venous blood sample for measurements of plasma Na⁺, K⁺, glucose, creatinine, NT-proBNP, BNP, serum insulin and also urinary cGMP and creatinine.
- Women of child bearing potential will have a urine pregnancy test to verify they are not pregnant. The 6 minute walk test will be performed in a 20 meter corridor.
- Measure BP three times and the average of those measurements will be recorded.
- fMRI and MRS will be performed in a 7 Tesla/90 cm whole-body actively shielded human scanner.

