5.2 Dosage and Administration

Entresto will be given orally at the recommended starting dose of 49/51 mg twice-daily. The dose of Entresto should be doubled after 2 to 4 weeks to the target maintenance dose of 97/103 mg twice daily, as tolerated by the patient ^{25,60}.

12 Weeks of Treatment

We will follow the recommended dosages as reported in the Entresto prescribing information sheet distributed by: Novartis Pharmaceuticals Corporation East Hanover, New Jersey 07936. Subjects will initiate with the recommended dose of 49/51 mg (sacubitril/valsartan) twice daily for two weeks. For

Table 1. Criteria to lower dosage or discontinuation of Entresto
1. Hypotension (symptomatic hypotension or orthostatic hypotension, or hypotension that requires treatment)
2. Renal failure. Increase in creatinine > 50% of baseline value.
3. Hyperkalemia. K ⁺ > 5.2 mEq/L
4. Falls (related to hypotensive episodes)
5. Angioedema
Hypotension = a decrease from baseline in sitting systolic blood pressure (SBP) of ≥ 20 mm Hg and a decrease in sitting SBP to < 90 mm Hg or symptoms.

patients not currently taking an angiotensin-converting enzyme inhibitor (ACEi) or an angiotensin II receptor blocker (ARB) or previously taking a low dose of these agents we will initiate treatment with the lowest dose available (24/26) (sacubitril/valsartan) twice daily. After two weeks of treatment the study physician will progressively increase to the target maintenance dose of 97/103 mg (sacubitril/valsartan). Each participant will receive a package with enough pills containing Entresto/placebo that will last until the following schedule visit. To assure adherence to the treatment,

patients will return all the packages with the empty vials at each study visit. Participating patients will be encouraged to follow their standard health care treatment and lifestyle recommendations prescribed

by their attending physician.

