- Arterial elasticity testing using applanation tonometry in the radial artery. Patients in the supine position will have electrodes placed in their chest to record an EKG, will have a blood pressure taken and arterial pulse wave will be recorded for 30 seconds in the radial artery.
- A graded exercise testing procedure to determine pain free and maximal walking duration will be performed. Participant's blood pressure and EKG will be measured before, during and for 6 minutes following the exercise test. Contraindications outlined by the American College of Sports Medicine to perform and to stop an exercise test will be followed.
- The 6 minute walk test will be performed in a 20 meter corridor. Patients will be asked to walk as quickly as they can along the corridor for 6 minutes to cover as much distance as possible. They will be allowed to stop if they have to, but will be encouraged to continue again as soon as they are able. During the time that the participant stops walking the clock will continue to run. At the end of test the distance covered is measured.
- A Walking Impairment Questionnaire (WIQ), a 36-item short-form health survey (SF-36), and Quality of Life Questionnaire (PAD-QOL) will be given to each participant.
- Body height and weight will be measured using standard anthropometric procedures.
- Total body lean and fat mass will be determined using bioelectrical impedance from Valhalla Scientific body comp scale®.

Visit 2 (Baseline 2/Randomization)

The second screening visit will take place within 48 hours of Visit 1. The following tests and procedures will be performed:

- Women of child bearing potential will have a urine pregnancy test to verify they are not pregnant.
- MRS and fMRI will be performed in a 7 Tesla/90 cm whole-body actively shielded human

scanner.

- IDS will randomize and dispense the treatment drug or placebo.
- The subject will be given instructions on how to take the drug and will be provided a diary to keep track of any adverse events they are experiencing.

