6.2 Treatment Period

Visits 3, 4 and 5 (Treatment visits at Weeks 2, 4 and 6)

Subjects will be required to return to the clinic at weeks 2, 4 and 6 of treatment to perform the following procedures and tests:

- Dose modification to target dose at week 2 and lowering of dose per direction of physician at weeks 4 and 6.
- Blood glucose, creatinine and potassium levels.
- Women of child bearing potential will have a urine pregnancy test to verify they are not pregnant.
- Blood pressure measurement and reading of recording on the blood pressure monitor.
- Review of daily diaries for any side effects.
- Collect and assess study medication; dispense study medication.

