6.5 Follow-up Visits

Visits 8 (Follow-up, Week 6 after End of Treatment Visit)

Subjects will return 6 weeks after their treatment has ended to assess if any changes have occurred in pain free walking duration, maximal walking duration during the 6 minute walking test. Subjects will have a Walking Impairment Questionnaire (WIQ) and Quality of Life Questionnaire (PAD-QOL) administered. The presence or absence of adverse events following withdrawal of study drug will be assessed.

Schedule of Events

Schedule of Events								
	Visit 1 Screening	Visit 2 Baseline	Study Visits 3-7					Follow-up Visit 8
Time Point		Day 0	Week 2	Week 4	Week 8	Week 12	Week 12	Week 18
Time estimates	4 hours	4 hours	1 hour	1 hour	1 hour	4 hours	4 hours	45 min
Obtain Consent	x							
Ankle brachial Index	x					x		
Duplex ultrasound ¹	x							
Arterial elasticity	X					X		
Questionnaires	x					x		x
Memory test	X							
Height, weight, lean and fat mass	X					X		
Treadmill test	x					x		x
6 minute walk	x	x					x	x
MRI		x					x	
Blood draw for labs	X	x	x	x	x	x	x	
Urine test		x					x	
Blood pressure ²	x	x	x	x	x	x	x	x
Pregnancy test ³	x	x	X	X	X	X	X	X
Receive drug/placebo		x	x	x	x			
Review blood pressure records and diary			x	x	x	x		

1. Screening visit could be 5 hours long if duplex ultrasound is required, if not it will last 4 hours.
2. Visit should occur within 24 hours of last dose of drug.
3. Blood draw at screening and end of treatment visit 1 are following 10 hour fasting to assess serum: creatinine and K⁺, sodium, glucose, and serum insulin. Study visits at weeks 2, 4 and 6 are also fasting 10 hours prior to blood draw to assess: serum glucose, creatinine and potassium.
4. Duplex ultrasound will be perform only on those patients without a duplex ultrasound for the diagnosis of renal artery stenosis within the last year.
5. NIH toolbox for cognitive function.

6. The treadmill GXT test will be used to determine pain free walking distance, maximal walking distance.
7. Subjects will be instructed to measure and record their blood pressure at home, 3 times daily during the treatment period.
8. For women of childbearing potential.

7. Data Handling and Record Keeping

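### The end-of-treatment 6-minute walk, MRI, BNP and urinary cGMP may be measured up to 72 hours after the last pill, because Section 6.4 states its 24-hour limit only for Visit 6

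*Combined protocol and SAP*

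**What the plan says.** End-of-treatment testing is split over two visits in Section 6.4. For Visit 6 the limit is tied to dosing: "Subjects will be asked to return within 24 hours of taking their last study pill". Visit 6 holds the ankle brachial index, the treadmill test and the questionnaires. For Visit 7 the limit is tied only to the previous visit: "Visit 7 will occur within 48 hours of visit 6". Visit 7 holds the 6-minute walk, fMRI and MRS, and the fasting sample with NT-proBNP, BNP and urinary cGMP. The Schedule of Events agrees: it marks the walk, the MRI and the urine test in the second Week 12 column.

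Four places bear on whether patients still take drug between the two visits:

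- Section 6.4, Visit 6, lists "Collect and assess study medication" and no dispensing. None is listed at Visit 7 either.
- Section 6.2, for the earlier treatment visits, lists "Collect and assess study medication; dispense study medication".
- Section 5.2 on supply: "Each participant will receive a package with enough pills containing Entresto/placebo that will last until the following schedule visit".
- The drug row of the Schedule of Events is marked at Day 0 and the next three treatment visits, and in neither Week 12 column.

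Footnote 2 to the Schedule of Events reads "Visit should occur within 24 hours of last dose of drug" and does not say which visit it means.

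**The concern.** The plan treats time since last dose as important enough to limit at Visit 6, then sets no such limit in Section 6.4 for the visit that holds a primary-objective measure and all the imaging. If dosing stops at Visit 6, patients on active drug are tested after a drug-free gap whose length varies with scheduling and which the plan does not ask anyone to record.

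Any effect that depends on current exposure would be weakened by an unknown amount:

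- **Urinary cGMP** is the clearest case. Section 1.1.4 calls it a marker of natriuretic peptide activity. A null result after an uncontrolled gap could not be told apart from wash-out.
- **The 6-minute walk** could be affected, because Section 1.1.3 expects vasodilation as well as slower changes.
- **Structural effects**, such as vascular growth, would probably lose little.
- **Secondary objective 1** relates functional change to microvascular and mitochondrial function. Treadmill results at up to 24 hours off drug could be related to imaging at up to 72 hours off drug.

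The treadmill outcomes, the stated power and the type I error are unaffected. The effect on secondary objective 2 is minor.

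**Working it through.** The plan states no total lag to Visit 7, so there is no figure of its own to reproduce on this point. Its one design calculation (Section 9.2: change 278 m, SD 240 m, power 0.85, alpha 0.05) gives 14.4 per group by a two-sided two-sample t-test, which rounds up to the stated 15. It rests on pain-free walking distance and does not enter below.

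**Maximum lag**

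| Input | Value | Source |
|---|---|---|
| Last pill to Visit 6 | at most 24 h | 6.4 |
| Visit 6 to Visit 7 | at most 48 h | 6.4 |
| Dosing interval | 12 h (twice daily) | 5.2 |

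- Visit 6: 24 h, and 24 / 12 = 2 dosing intervals.
- Visit 7: 24 + 48 = 72 h, and 72 / 12 = 6 dosing intervals.
- With the 24 h limit applied to Visit 7 as well, the ceiling falls from 72 h to 24 h.

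**Does dosing stop at Visit 6?** No sentence says so. Section 6.4 places the last pill before Visit 6. Drug is collected and not re-issued there, whereas earlier visits do both. Packages are sized to reach the next visit, and the schedule issues nothing at Week 12. All four point the same way, and nothing in Section 6.4 provides for a dose between the two visits.

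**Baseline comparison.** Section 6.1 has the same split: "The second screening visit will take place within 48 hours of Visit 1". It raises no wash-out question, because drug is first issued at that second visit: "IDS will randomize and dispense the treatment drug or placebo".

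**How much effect could be lost.** The documents give no offset data. For illustration only, assume exponential offset, so that the share remaining is 2^(−t / half-life), with assumed half-lives:

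| Assumed effect half-life | Left at 24 h | Left at 72 h |
|---|---|---|
| 12 h | 25.0% | 1.6% |
| 24 h | 50.0% | 12.5% |
| 48 h | 70.7% | 35.4% |
| 4 weeks (672 h) | 97.6% | 92.8% |

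The loss would be near total for a fast effect and trivial for a slow one.

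**The case against.** The strongest reply is that footnote 2 may already close the gap. Only three footnote markers survive in the extracted table, against eight notes, and they sit on rows whose content matches other notes. Footnote 2 concerns a visit rather than a test, so it may have marked one or both Week 12 columns. This stands as a real uncertainty. If the note covers Visit 7, it is compatible with Section 6.4 and supplies the missing limit. Section 6.4 should then say so, and collecting drug at Visit 6 would work against it.

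The other points are fair and limit the size of the concern:

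- **Wash-out is inferred.** Both visits are headed as end of treatment, and no sentence stops dosing. The inference is still the most natural reading of four separate places.
- **72 hours adds two maxima.** Nothing suggests that the ceiling is typical.
- **The half-lives are assumed.** A range from 2% to 93% remaining cannot show whether the harm is serious or negligible.
- **BNP and urinary cGMP appear in no stated objective**, and Section 9.1 gives them no specific analysis. The walk is in the primary objective, however, and imaging carries secondary objective 1.
- **Slow effects may dominate.** The rationale stresses mitochondrial and vascular growth, and secondary objective 2 follows walking gains for weeks after withdrawal. Any attenuation would also bias towards no effect.

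The schedule marks a blood draw in both Week 12 columns, and footnote 3 places a fasting draw at the first end-of-treatment visit. That note does not list BNP or cGMP, so it does not rescue those measures.

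**Conclusion.** The concern holds. Followed as written, Section 6.4 permits a drug-free gap of variable length, up to 72 hours, before the 6-minute walk, fMRI/MRS, BNP and urinary cGMP, against at most 24 hours for the treadmill test.

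This rests on two assumptions: that dosing ends by Visit 6, which the supply and collection instructions support but no sentence states, and that footnote 2 does not cover Visit 7, which the available table cannot settle. The resulting loss of effect cannot be calculated from the documents and may be small for the walk and the imaging. It is most plausible for urinary cGMP.

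The change should be made, because a gap before testing cannot be undone after data collection and costs little to prevent now. Confidence is medium.

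**What to change.** 1. Continue study drug until Visit 7, and say so in Section 6.4.
2. Issue enough drug at the last treatment visit to cover it. From Week 6 (Section 6.2) that is 42 days × 2 = 84 doses, or 88 with the extension. From Week 8 (Schedule of Events) it is 28 × 2 = 56 doses, or 60 with the extension.
3. Move the final medication collection and pill count from Visit 6 to Visit 7, and repeat the diary review there.
4. State in Section 6.4 and in footnote 2 that both Week 12 visits take place within 24 hours of the most recent dose.
5. Record hours since last dose at each end-of-treatment assessment.

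This works whichever visit holds the walk. It makes no claim about matching baseline and end-of-treatment visits.

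**Cost.** No added visits or tests. Exposure rises by at most 48 / 12 = 4 doses per patient, or 4 × 30 = 120 doses of active drug or placebo across the trial. That is 2 days on top of 84, or 2.4%. The pill count comes later and one diary check is repeated. Potassium and creatinine are already drawn at Visit 7, so the extra days stay covered by safety laboratory tests.

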9.1 Statistical Methods

General baseline characteristics will be described using mean and proportions. Smirnov-Kolmogorov tests will be used to test normality of distribution of variables. For variables that do not follow the normal distribution, log transformation will be performed. Linear simple and multiple regressions will be performed to assess

association between the effects of Entresto on metabolic and physiological changes with clinical functional variables. Differences between the placebo and the

Entresto group will be assessed using independent sample t-test and Chi-square for quantitative and categorical variables, respectively. Change following the 12 week clinical trial in metabolic and physiological parameters will be assessed using paired sample t-test. Repeated measures analysis of covariance will also be used to evaluate differences between groups as a function of time. A p value < 0.05 will be used to determine statistical significance. Effect size (EF) calculated as $EF = (\text{mean Entresto group} - \text{mean placebo}$

group)/SD (control group) will be used to assess the clinical significance of the effects of Entresto⁶³. The PI will be in charge of performing all statistical calculations using SAS v 9.3 by SAS Institute Inc., Cary, NC. [name] Jr. Professor at the School of Public Health a statistician with more the 800 publications will be a consultant in statistical analysis of the data.

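### The visit lists and the Schedule of Events disagree on fasting and walking on the two MRS/fMRI days, and the planned within-arm paired tests cannot separate a drug effect from unmatched scan conditions

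*Combined protocol and SAP*

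**What the plan says.** All references are to the combined protocol and SAP.

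- **Baseline scan day, section 6.1, Visit 2.** The list has "MRS and fMRI will be performed in a 7 Tesla/90 cm whole-body actively shielded human" scanner, a pregnancy test, randomization and dispensing, instructions and a diary, and the home blood pressure monitor. It has no fast, blood draw or 6-minute walk. Those are listed at Visit 1, and "The second screening visit will take place within 48 hours of Visit 1".
- **Week 12 scan day, section 6.4, Visit 7.** The list has a "10 hour fasting venous blood sample for measurements of plasma" electrolytes and other analytes. It also says "The 6 minute walk test will be performed in a 20 meter corridor" and "fMRI and MRS will be performed in a 7 Tesla/90 cm whole-body actively shielded human" scanner.
- **Schedule of Events, section 6.5.** The walk row begins "6 minute walk x x", so it is marked at Visit 1 and at Visit 2. A blood draw and a urine test are also marked at Visit 2. The second Week 12 visit carries the same three items.
- **Footnote 3 to the Schedule.** "Blood draw at screening and end of treatment visit 1 are following 10 hour fasting". It adds the treatment visits at weeks 2, 4 and 6. It names neither Visit 2 nor Visit 7.
- **Section 9.1.** "Change following the 12 week clinical trial in metabolic and physiological parameters will be assessed using paired sample t-test". The same section plans an independent-sample t-test between Entresto and placebo, a repeated measures analysis of covariance, and regressions relating metabolic and physiological changes to functional ones.

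**The concern.** The MRS and fMRI endpoints are resting PCr and pH, PCr recovery, and reoxygenation of two calf muscles. The patients have exercise-induced leg symptoms, so a walking test on the scan day, or a different prandial state, is a plausible influence on what is measured. Followed literally, the visit lists give a Week 12 scan on a day with a fast and a walk, and a baseline scan on a day with neither.

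A within-arm paired test attributes all of the mean change to the 12 weeks of treatment. If scan conditions also changed, the test could show an improvement that the drug did not cause, or hide one that it did. Section 9.1 does not label these tests descriptive or rank them below the between-group tests. Secondary objective 1 also uses the metabolic changes as variables in a regression with 30 patients, so avoidable noise in them matters.

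**Working it through.** **Step 1. The passages side by side**

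| Item | Visit 2, list in 6.1 | Visit 2, Schedule | Visit 7, list in 6.4 | Second Week 12 visit, Schedule |
|---|---|---|---|---|
| MRS/fMRI | yes | yes | yes | yes |
| 6-minute walk | not listed | marked | listed | marked |
| Blood draw | not listed | marked | listed | marked |
| 10-hour fast | not listed | not in footnote 3 | listed | not in footnote 3 |
| Order of walk and scan | – | not stated | not stated | not stated |

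On the lists alone, the scan days differ in both the walk and the fast. On the Schedule alone, they match in walk and blood draw, and fasting is unstated for both. The end-of-treatment fast is itself in conflict: section 6.4 puts it at Visit 7 and lists no blood draw at Visit 6, while footnote 3 puts it at Visit 6. The treadmill is affected too. It is done at Visit 1 (fasted) and at Visit 6, which is fasted under footnote 3 but has no stated fast under section 6.4.

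**Step 2. The plan's own figure**

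Section 9.2 gives a change of 278 m, SD 240 m, power 0.85, type I error 0.05 and 15 per group. The standardised difference is 278/240 = 1.158. Taking a two-sided two-sample t-test, the noncentrality at n per arm is 1.158 × √(n/2).

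- n = 14: 3.065, power 0.839
- n = 15: 3.172, power 0.865

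So 15 per group reproduces. This point does not dispute it, and takes n = 15 per arm from it.

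**Step 3. Within-arm paired test, no drug effect**

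Let s be the shift caused by scan conditions, in SDs of the change score. The documents give no value for s, so every non-zero value here is an assumption. The test statistic has a noncentral t distribution with 14 degrees of freedom and noncentrality s × √15. The two-sided 5% critical value is 2.145.

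| s | s × √15 | Rejection rate |
|---|---|---|
| 0 | 0 | 5.0% |
| 0.25 | 0.968 | 14.7% |
| 0.5 | 1.936 | 43.8% |
| 0.8 | 3.098 | 82.1% |

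**Step 4. Between-group test, no drug effect**

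Both arms follow the same visits. If each arm's mean change is shifted by s, the difference between arms is s − s = 0. A simulation of the independent t-test on change (15 per arm, 100,000 runs, s of 0, 0.2, 0.5, 0.8 and 1.0) gave rejection rates from 4.9% to 5.1%.

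**Step 5. Variation between patients**

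A shift that is the same for everyone leaves regression slopes unchanged. A shift that varies from patient to patient does not cancel: it enlarges the SD of the change scores, which affects both the between-group tests and the regressions for secondary objective 1. An unspecified order and interval between walk and scan permits this. Its size cannot be derived from the documents.

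**The case against.** The strongest reply is that the Schedule already matches the two scan days: each carries an MRI, walk, blood draw and urine test. Section 3.2 also asks for a 10-hour fast before the blood panel that includes NT-proBNP and BNP. The Visit 1 list omits those two analytes, so their baseline values may have been meant for a fasted Visit 2. This inference is fair, and it means that fasting at Visit 2 is unstated rather than excluded. A reader of the visit lists might conclude that the baseline scan day definitely has neither fast nor walk. The documents do not support that.

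A reader might also infer that the Week 12 scan follows the walk and so images a recently ischaemic calf. No passage gives the order, and the lists are not evidently chronological: at Visit 6 the pregnancy test comes last, after the treadmill test. Section 4.2 describes claudication as relieved by rest, and section 3.8 has a 5-minute rest before the scanner. Carry-over is therefore possible but not shown.

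Finally, the trial is randomized and plans between-group tests, which an additive shift common to both arms does not bias. This stands in full.

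What the reply does not remove is the contradiction between the passages, the absence of any rule on prandial state or order at scanning, and the planned paired tests, which are exposed if the lists are what staff follow.

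**Conclusion.** The point holds as an inconsistency with a conditional statistical consequence. The documents disagree on the content of Visits 2, 6 and 7. If the visit lists govern, baseline and Week 12 scan conditions differ, and the within-arm paired t-tests cannot tell that difference from a drug effect. If the Schedule governs, the walk mismatch disappears, but prandial state and the order of walk and scan remain open.

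The range of about 15% to 44% false rejection rests on n = 15, two-sided testing at 5%, no drug effect and an assumed shift of 0.25 to 0.5 SD. It illustrates how sensitive the paired test is and is not an estimate of what will occur. A reader might infer that the Entresto-versus-placebo comparison of MRS/fMRI is biased. It is not, for an additive shift common to both arms. Extra noise, or an interaction between scan conditions and drug, would remain. The affected measures serve secondary objective 1, and the correction is cheap, so it should be made.

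**What to change.** 1. Reconcile the Visit 2 list in section 6.1, the Visit 6 and 7 lists in section 6.4, and the Schedule of Events with its footnote 3, so that each procedure and the fast appear at the same visit everywhere.
2. State one prandial state for both scans, and do the MRI before the 6-minute walk at both Visit 2 and Visit 7.
3. State one prandial state for the treadmill tests at Visits 1 and 6.
4. In section 9.1, name the between-group comparison of change as the inference for MRS and fMRI, and label the within-arm paired tests descriptive.

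The cost is a text correction and some reordering within existing visits. The patient may have to come fasted on the baseline scan morning. Scanning first is a choice that removes the walk as an influence; the documents do not themselves require it.
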